### **Non-target lesions**

Non-target lesions will be assessed at each post-baseline timepoint individually and as a group. Response categories are as defined below:

- Absent/Normalized (CR): All individual non-target nodal lesions must have returned to normal size. All extranodal lesions must have disappeared.
- Unequivocal Progression (PD): Any individual non-target lesion must unequivocally progress in the context of the overall disease burden to be assessed as PD. For increased thickening of the wall of a hollow viscus, the reviewer will use their cautious judgment to determine whether the increase is most likely caused by disease progression.

PD should not be called based solely on enlarging pleural effusions or ascites, or enlarging lytic bone lesions. Rather, the overall assessment should be based on the rest of the disease burden.

- SD: At least 1 non-target lesion is still present, or a lymph node enlarged, without any individual lesions showing unequivocal progression.
- NE: When an individual non-target lymph node, extranodal lesion, or non-measurable disease manifestation cannot be assessed at a post-baseline timepoint due to missing imaging, poor image quality, changes in the lesion or background that precludes assessment, or focal therapy to a lesion, the individual non-target lesion will be assessed as NE. The assessment of the non-target lesions as a whole will be NE if any of the non-target lesions are NE and none are PD.

### **New lesions**

Lesions will be considered new if they were not present at the baseline timepoint but are visible at the current timepoint.

A node will be recorded as a new lesion if it was previously normal in size and is now >1.5 cm in LDi. An unequivocal, new extranodal lesion of any size is considered a new lesion. If multiple new lesions are noted, at least one should be documented individually as a new lesion.

New lesions must be strongly believed to be due to CLL rather than another etiology (eg, infection, inflammation).

Some types of truly non-measurable lesions generally require further verification that they are attributable to CLL through biopsy or cytology. These include ascites, pleural or pericardial effusions, and lytic bone lesions. They should be recorded as new lesions only when there is other evidence of progression.

Other truly non-measurable lesions will not require verification to be considered a new lesion, as long as their appearance is unequivocal in the judgment of the reviewer:

- Non-measurable lesions in the central nervous system, attributable to CLL
- Non-measurable nodal masses such as infiltrative mesenteric or retroperitoneal masses

Extranodal lesions which disappeared and then reappeared at a later timepoint will cause a determination of progression, just like a new lesion, but are not designated “new”.

The combined focal lesion response will be determined as follows:

#### Lymph Node Response

Target	Non-target	New lesions	Lymph Node Response
CR	CR	No	CR
CR	SD	No	PR
PR	CR/SD	No	PR
SD	CR/SD	No	SD
Any non-PD	NE	No	NE
NE	Any non-PD	No	NE
PD	Any	Yes/No	PD
Any	PD	Yes/No	PD
Any	Any	Yes	PD
NA	NA	No	NED
Abbreviations: CR=complete response; NA=not applicable – (no lesions of this type present at baseline); NE=not evaluable; NED=no evidence of disease – (no lesions of any kind seen at baseline, and none present at visit being evaluated); PD=progressive disease; PR=partial response; SD=stable disease.			

#### Spleen response

The spleen will be measured in the craniocaudal length as at baseline, and the enlarged portion calculated by subtracting 12.9 cm. Response categories for the spleen are as defined below:

- Normal (CR): Spleen was enlarged at baseline and has regressed to <13 cm at the current timepoint, or the spleen was assessed as normal at baseline and is still normal, or there is radiological evidence of splenectomy at baseline, or the spleen was normal at baseline, and there has been a splenectomy since then.
- PR: Spleen was assessed as enlarged at baseline, and its excess length has decreased by  $\geq 50\%$ .
- SD: No decrease consistent with PR and no increase consistent with progression.

- PD: The spleen is assessed as showing PD if any of the following are true:
  - Recurrent splenomegaly: A spleen which was abnormal at baseline ( $\geq 13$  cm) first returned to normal, but at the current timepoint the spleen has increased by  $\geq 2$  cm from its nadir and the length is  $\geq 13$  cm.
  - New splenomegaly: No prior splenomegaly. The spleen has increased by  $\geq 2$  cm from baseline and the length is  $\geq 13$  cm.
  - Progression of existing splenomegaly: A spleen which was abnormal at baseline has the enlarged portion increase by  $\geq 50\%$  at the current timepoint from its nadir value, and  $\geq 1$  cm in absolute length.

### **Liver response**

The liver will be assessed qualitatively. Response categories are defined below:

- Normal (CR): Liver was assessed as enlarged at baseline and has regressed to a normal size, OR liver was assessed as normal at baseline and continues to be normal in size.
- SD: Liver is considered stable when it is qualitatively enlarged, without unequivocal increase, on the basis of CT and/or MRI scans.
- Unequivocal increase (PD): New hepatomegaly, recurrent hepatomegaly, or clear progression of existing hepatomegaly.

### **Liver and Spleen Response**

The liver and spleen should be assessed together for a response at each post-baseline timepoint based on the following table.

## Post-baseline Liver and Spleen Assessment

Liver	Spleen	Liver & Spleen Response
Normal	Normal (<13 cm)	CR
Normal Enlarged but stable	PR (enlarged portion decreased $\geq 50\%$ )	PR
Enlarged but stable	CR (spleen went from enlarged to normal)	PR
Enlarged but stable	Remains normal	SD
Went from enlarged to normal	Stably enlarged	PR
Remains normal or Enlarged but stable	Stably enlarged	SD
Any except progression	NE	NE ( extremely unlikely )
NE	Any except progression	NE ( extremely unlikely )
Progression Newly enlarged or Definite growth from prior timepoint	Any	PD
Any	Progression 50% increase from baseline ( $\geq 1$ cm increase) Regrowth of prior splenomegaly ( $\geq 2$ cm increase) New splenomegaly ( $\geq 13$ cm and $\geq 2$ cm increase)	PD
Abbreviations: CR=complete response; NE=not evaluable; PD=progressive disease; PR=partial response; SD=stable disease. Note: To be considered “enlarged” for the purposes of this assessment, the liver must be enlarged (qualitative assessment by experienced reviewer) without any non-malignant explanation for the enlargement.		

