### **Spleen Assessment at Baseline**

Splenic disease will be assessed quantitatively, independent of the assessment of measurable and non-measurable focal lesions. The spleen will be measured in the cranial to caudal axis, and all spleen measurements referred to hereafter will refer to this craniocaudal length. The spleen is considered normal if the length is less than 13 cm (or if the spleen has been removed surgically). It is considered enlarged if it is greater than or equal to 13 cm in length. The portion of the measurement that exceeds 12.9 cm will be referred to as the abnormal portion, or the excess length.

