### 10.9.1.4 iwCLL Summary Table

The following table summarizes the assessments based on both imaging and hematological parameters [Hallek, M., et al 2018].

Group	Parameter	Complete Response	Partial Response	Progressive Disease	Stable Disease
A	Lymph nodes	CR (see lymph node response table)	PR (see lymph node response table)	PD (see lymph node response table)	SD (see lymph node response table)
	Liver and/or spleen size	CR (see liver and spleen response table)	PR (see liver and spleen response table)	PD (see liver and spleen response table)	SD (see liver and spleen response table)
	Constitutional symptoms	None	Any	Any	Any
	Circulating lymphocyte count	Normal	Decrease $\geq 50\%$ (from screening)	Increase $\geq 50\%$ (from nadir)	Change of -49% to +49%
B	Platelet count	$\geq 100 \times 10^9/L$	$\geq 100 \times 10^9/L$ or increase $\geq 50\%$ over screening	Decrease $\geq 50\%$ (from screening secondary to CLL)	Change of -49% to +49%
	Hemoglobin	$\geq 11.0$ g/dL (untransfused and without erythropoietin)	$\geq 11.0$ g/dL or increase $\geq 50\%$ over screening	Decrease $\geq 2$ g/dL (from screening secondary to CLL)	Increase $< 11$ g/dL or $< 50\%$ over screening or decrease $< 2$ g/dL
	Marrow	Normocellular, no CLL cells, no B-lymphoid nodules	Presence of CLL cells, or of B-lymphoid nodules or not done	Increase of CLL cells by $\geq 50\%$ on successive biopsies	No change in marrow infiltrate
	Neutrophils	$\geq 1.5 \times 10^9/L$ (no exogenous growth factors)	Non-CR (Not meeting criteria for CR)	Non-CR (Not meeting criteria for CR)	Non-CR (Not meeting criteria for CR)
Abbreviations: CLL=chronic lymphocytic leukemia; CR=complete response; PD=progressive disease; PR=partial response; SD=stable disease.					

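### For CLL/SLL, Appendix 9 measures progression of existing splenomegaly from nadir in the text but from baseline in the response table, so the same scan can be PD by one and PR or SD by the other

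*Combined protocol and SAP*

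**What the plan says.** All of this concerns CLL/SLL under the iwCLL criteria in Appendix 9.

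- **Excess length (Section 10.9.1.2.1).** "The portion of the measurement that exceeds 12.9 cm will be referred to as the abnormal portion, or the excess length".
- **Text (Section 10.9.1.2.2, Spleen response).** For a spleen already enlarged at baseline, PD needs the enlarged portion to grow by at least 50%, "at the current timepoint from its nadir value", and by at least 1 cm. PR is defined thus: "Spleen was assessed as enlarged at baseline, and its excess length has decreased by" at least 50%. Recurrent splenomegaly, a rise of at least 2 cm from nadir, applies only to a spleen that had first returned to normal.
- **Table (Post-baseline Liver and Spleen Assessment).** The spleen PD cell reads "Progression 50% increase from baseline", with an increase of at least 1 cm. A second line, "Regrowth of prior splenomegaly", asks for an increase of at least 2 cm but names no reference point and does not require earlier normalisation. The PR cell reads "PR (enlarged portion decreased" by at least 50%.
- **Which one assigns the response.** Liver and spleen "should be assessed together for a response at each post-baseline timepoint based on the following table". The iwCLL summary table (Section 10.9.1.4) sends the reader to the same place: "PD (see liver and spleen response table".
- **Consequence of a spleen PD.** Under Section 10.9.1.3, one progressing parameter is enough for overall PD. That ends DOR (Section 9.4.2) and PFS (Section 3).

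**The concern.** The two reference points coincide only when the spleen never shrank. Once it has shrunk without returning to normal, nadir lies below baseline, and regrowth reaches the nadir threshold before the baseline threshold. These are largely the participants with a response, so the disagreement falls on those who contribute to DOR.

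Response is assessed by the investigator and the synopsis lists no adjudication committee. Nothing in the plan ensures that two sites would apply the same rule to the same scan. At stake is the date of progression for a secondary endpoint and an exploratory one. Progression also governs discontinuation of treatment (Sections 7.1 and 8.2.2.1.1), so the inconsistency reaches beyond the analysis.

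**Working it through.** The plan gives no figure on this point to reproduce. The check applies both rules to the same spleen lengths.

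**Inputs.** Let b, n and c be the baseline, nadir and current lengths in cm, with enlarged portion E = length − 12.9. The spleen is enlarged at baseline and never normalises, and the liver is normal throughout.

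**Rules.**
- Text PD: E(c) ≥ 1.5 × E(n) and c − n ≥ 1.
- Table 50% line, applied to the enlarged portion: E(c) ≥ 1.5 × E(b) and c − b ≥ 1.
- Table regrowth line, narrow reading: only spleens that had normalised, so it never fires here. Broad reading: any c − n ≥ 2.
- Spleen PR, text and table: E(c) ≤ 0.5 × E(b).

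**Main example, 20.9 → 14.9 → 16.4 cm.** E = 8.0 → 2.0 → 3.5.
- Text: 3.5 / 2.0 − 1 = +75%, and 16.4 − 14.9 = +1.5 cm, so PD. The threshold was 12.9 + 3.0 = 15.9 cm.
- Table: 3.5 / 8.0 − 1 = −56%, so PR. The regrowth line is not met even when read broadly, since 1.5 < 2. The 50% line is first met at 12.9 + 1.5 × 8.0 = 24.9 cm, or at 1.5 × 20.9 = 31.35 cm if the 50% refers to the whole length.

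**Further cases.**

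| Lengths b → n → c (cm) | E (cm) | Text | Table, regrowth narrow | Table, regrowth broad |
|---|---|---|---|---|
| 20.9 → 14.9 → 16.4 | 8.0 → 2.0 → 3.5 | PD | PR | PR |
| 15.1 → 13.0 → 14.0 | 2.2 → 0.1 → 1.1 | PD | PR | PR |
| 15.0 → 13.0 → 14.0 | 2.1 → 0.1 → 1.1 | PD | SD | SD |
| 20.9 → 14.9 → 18.9 | 8.0 → 2.0 → 6.0 | PD | SD | PD |
| 22.9 → 20.9 → 22.9 | 10.0 → 8.0 → 10.0 | not PD (+25%) | SD | PD |

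**Direction of the 50% line alone.** Because n ≤ b, meeting 1.5 × E(b) implies meeting 1.5 × E(n), and c − b ≥ 1 implies c − n ≥ 1. So this line never calls PD before the text does.

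A 0.1 cm grid agrees (baseline 13.0 to 25.0, nadir 13.0 to baseline, current nadir to 30.0; 966,911 combinations):
- PD by the 50% line but not by the text: 0.
- PD by the text but not by the 50% line: 428,808. In 40,570 of these the table gives PR.
- Of those 40,570, still in conflict when regrowth is read broadly: 17,610.

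These counts show that the conflict can occur; they are not frequencies in patients.

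**Direction with regrowth read broadly.** Every rise of 2 cm or more from nadir is PD, so a late call is possible only for rises of 1 to under 2 cm. An early call is possible when 2 cm is less than half the nadir enlarged portion, that is E(n) > 2 / 0.5 = 4.0 cm, or a nadir length above 16.9 cm. The last row is such a case.

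**Delay.** A PD missed at one scheduled assessment is called at the next at the earliest. Section 8.2.2 sets 12 weeks between assessments, with 24 weeks allowed from the fourth year; imaging can be more frequent if clinically indicated.

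**The case against.** The best defence is that the table is shorthand. Section 10.9.1.1 describes the tables as summaries and the following sections as the detail, and the table takes as input spleen categories that the text defines. That makes the nadir rule the natural reading, but it is not a statement of precedence. Two other places send the assessor to the table, and its words give a different rule.

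A reader might infer that using the table always overstates DOR and PFS, because the spleen would have to pass the 50% line before PD is called. The documents do not support that. The regrowth line sits in the same cell, and on its plain words it catches any rise of 2 cm or more: 20.9 → 14.9 → 16.9 cm would be PD. Read that way, the table can also call PD before the text does. Nor does the 50% line require the spleen to be half as large again as before treatment: 24.9 / 20.9 = 1.19, a 19% rise in length. Only the enlarged portion rises by half.

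A reader might also infer that the mismatch is what lets a spleen satisfy PR and PD at one visit. The text alone allows that, since its spleen PR rule has no exclusion for progression from nadir. Section 10.9.1.3 settles it for overall response, because PD in any parameter prevails. The real conflict is between text and table.

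The stakes are also limited. Enrolment is about 6 to 12 across all histologies, no hypothesis is tested, and Section 9.6.2 summarises DOR only if there are enough responders. This bears on importance and does not remove the contradiction.

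**Conclusion.** The contradiction is real and should be corrected. Text and table give different reference points for the same event, and neither reading of the regrowth line removes the conflict for rises of 1 to under 2 cm from nadir.

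The effect on the endpoints is conditional. It arises only in a CLL/SLL participant with splenomegaly that shrank without normalising, and only where spleen regrowth is the first sign of progression. Under the table's 50% line alone, PD is then dated at the same visit or later, by at least one scheduled assessment when it differs, and DOR and PFS are equal or longer. With regrowth read broadly, the shift can go either way. A general claim of inflation is therefore not established.

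The total effect cannot be computed, because neither the number of CLL/SLL participants nor their spleen measurements are given. With so few responders, a single redated event could move a Kaplan-Meier median. DOR is secondary and PFS exploratory; the primary safety endpoints are untouched.

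**What to change.** Reconcile the spleen text in Section 10.9.1.2.2 with the Post-baseline Liver and Spleen Assessment table, so that both state:

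1. One reference point for progression of existing splenomegaly, and whether the 50% applies to the enlarged portion. For comparison, the CLL target-lesion and lymphocyte rules and both Lugano statements for existing splenomegaly (Sections 10.9.2.2 and 10.9.2.3.2) use nadir; the CLL platelet and haemoglobin rules use baseline.
2. One definition of regrowth, with its reference point, and whether it is limited to spleens that had returned to normal, as the text has it.

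Then re-derive the CLL/SLL spleen calls for DOR and PFS from the recorded craniocaudal lengths under that single rule, and report any progression date that changes.

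Because progression also governs stopping of treatment, the sponsor must settle the clinical use of the rule when reconciling the two places; this review does not choose it. The cost is a few words in one table cell and a re-check of spleen lengths already collected. No new data are needed.

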## Clinical data

At each follow-up timepoint, constitutional symptoms, circulating lymphocyte count, platelet count, neutrophil count, hemoglobin, and bone marrow will also be considered as part of the response assessment.

## Constitutional Symptoms

Participants will be evaluated for the presence of fever ( $\geq 38.0^{\circ}\text{C}$ ), night sweats, weight loss and significant fatigue at every follow up timepoint.

### Blood Count and Bone Marrow Assessments

Hemoglobin, platelets, neutrophils, lymphocytes will be assessed at each follow up timepoint and results will be incorporated into the overall response. At certain protocol-specified time points, additional tissue biopsies may be collected and incorporated into the response assessment.

### Physical examination findings

On rare occasions, lesions may be present on physical examination that are not seen on imaging at all. An example might be lymphadenopathy in the popliteal fossa, when the “whole body” imaging includes only anatomy to the mid femur. Such lesions should be documented as non-target lesions in study forms. They can contribute to progression if new lesions appear this way, and if any were present at baseline, they must disappear for an overall response of CR. If imaging was not performed, but the spleen and liver were assessed by physical examination, they can be used to contribute to the response assessment, in a qualitative manner only.

#### **10.9.1.3 Overall Response**

The imaging and clinical parameters are classified into 2 groups (A and B) and these groups will be assessed for response. Group A includes lymph node response, liver and spleen response, constitutional symptoms, and lymphocyte count. Group B includes platelet count, hemoglobin and bone marrow assessment.

### Response Category Definitions

**Complete Response (CR):** All criteria from both groups have to be met.

- Group A:
  - All lymph nodes (none  $\geq 1.5$  cm)
  - Liver and spleen are normal
  - Participant should have no constitutional symptoms
  - Circulating lymphocyte count is normal ( $<4 \times 10^9/L$ )
- Group B:
  - Platelet count  $\geq 100 \times 10^9/L$
  - Hemoglobin  $\geq 11.0$  g/dL (untransfused and without erythropoietin)

- Neutrophils  $\geq 1.5 \times 10^9/\text{L}$  (without exogenous growth factors)
- Normocellular marrow with no CLL cell or B-Lymphoid nodules

***Complete Response with Incomplete Marrow Recovery (CRi)***

CRi is defined as a CR with an incomplete recovery of the study participant's bone marrow. Study participants who have a CRi fulfill the criteria for a CR (including bone marrow examinations), but continue to have persistent anemia, thrombocytopenia, and/or neutropenia apparently unrelated to CLL, but related to drug toxicity.

**Nodular Partial Response (nPR)**

nPR is assessed when criteria for CR are met, except that bone marrow biopsy shows lymphoid nodules, reflecting residual disease (normocellular or hypocellular,  $<30\%$  lymphocytes and lymphoid nodules present).

**Partial Response (PR):** At least 2 parameters from Group A and 1 parameter from Group B improve from screening if they were abnormal at previous timepoints. If only 1 of the parameters in each group was abnormal, only one needs to improve. Improvement is described as the following:

- Group A:
  - PR in lymph nodes ( $\geq 50\%$  decrease in SPD)
  - PR in liver/spleen size (see above)
  - $\geq 50\%$  decrease in circulating lymphocyte count from baseline
  - Resolution of constitutional symptoms
- Group B:
  - Platelet counts should be  $\geq 100 \times 10^9/\text{L}$  or increase  $\geq 50\%$  from baseline
  - Hemoglobin  $\geq 11 \text{ g/dL}$  or  $\geq 50\%$  increase from baseline
  - Marrow: Presence of CLL cells, or of B-lymphoid nodules, or not done

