### 6.5.1 Prohibited Concomitant Medications

The following medications are not allowed during the screening and treatment phase of the study:

- Primary prophylactic G-CSF during the DLT evaluation period.
- Immunosuppressive therapies including continuous high-dose corticosteroids (>30 mg prednisone equivalent per day).
- Any concurrent anticancer therapy including, but not limited to, chemotherapy, radiotherapy (except palliative radiotherapy for local pain control), hormonal therapy or immunotherapy.
- Other investigational agents.
- Live or live attenuated vaccines within 30 days before the first dose of study intervention and while participating in the study.

NOTE: Any licensed COVID-19 vaccine (including for Emergency Use) in a particular country is allowed in the study as long as they are mRNA vaccines, replication incompetent adenoviral vaccines, or inactivated vaccines. These vaccines will be treated just as any other concomitant therapy. Investigational vaccines (i.e., those not licensed or approved for Emergency Use) are not allowed.

- Concomitant medications with the following characteristics are prohibited during the study (see Section 2.2.2.2 for DDI risk summary):
  - P-gp substrates with a narrow therapeutic index
  - CYP3A strong inducers
  - CYP3A strong inhibitors

Note: If the participant requires short-term use of CYP3A strong inhibitors, consultation with the Sponsor is required and treatment interruption with nemtabrutinib may be permitted.

Note: Detailed information of P-gp substrates with a narrow therapeutic index, CYP3A strong inducers and CYP3A strong inhibitors can be found at the following website:

<https://www.fda.gov/drugs/drug-interactions-labeling/drug-development-and-drug-interactions-table-substrates-inhibitors-and-inducers>

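### For CLL/SLL, the Group B part of partial response can be met by a transfused or erythropoietin-supported hemoglobin, or by a marrow never examined, so ORR can be overstated

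*Combined protocol and SAP*

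**What the plan says.** Section 10.9.1.3 splits the CLL/SLL response parameters into Group A (nodes, liver and spleen, constitutional symptoms, lymphocyte count) and Group B (platelets, hemoglobin, marrow). PR is defined by "At least 2 parameters from Group A and 1 parameter from Group B improve from screening if they were abnormal at previous timepoints", relaxed by "If only 1 of the parameters in each group was abnormal, only one needs to improve".

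For CR, hemoglobin of at least 11.0 g/dL must be "untransfused and without erythropoietin", and neutrophils must reach their threshold "without exogenous growth factors". The summary table in Section 10.9.1.4 repeats both conditions.

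For PR, the table asks for hemoglobin of at least 11.0 "g/dL or increase $\geq 50\%$ over screening", with nothing about support, and the text agrees. The PR platelet line ("Platelet counts should be" at or above 100 × 10⁹/L, or up by at least 50%) is also unconditional. The third Group B entry in the PR improvement list is a marrow that contains CLL cells or B-lymphoid nodules, or was not done.

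Section 9.4.2 counts a participant as an objective responder from PR upwards. Section 9.6.2 reports the rate with an exact 95% Clopper-Pearson interval.

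**The concern.** Group B is there to show that blood or marrow function has improved. A transfused or erythropoietin-driven hemoglobin does not show that, and the protocol accepts this reasoning for CR but does not apply it to PR. A marrow that was not examined shows nothing either way.

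Supported counts are foreseeable here. Section 5.1 lists hemoglobin below 10 g/dL and platelets below 100 × 10⁹/L among the reasons to treat CLL/SLL. Table 3 admits hemoglobin from 8.0 g/dL and waives the hemoglobin and platelet floors when marrow involvement is significant. PR is the entry point to objective response. If the rule can be read in two ways, two sites could score the same participant differently, and in a study this small one such case is visible in the reported rate.

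**Working it through.** **Step 1. The Group B criteria side by side (Sections 10.9.1.3 and 10.9.1.4).**

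| Item | CR | PR |
|---|---|---|
| Hemoglobin | ≥11.0 g/dL, no transfusion, no erythropoietin | ≥11 g/dL or ≥50% rise, no support condition |
| Platelets | ≥100 × 10⁹/L, no support condition | ≥100 × 10⁹/L or ≥50% rise, no support condition |
| Neutrophils | ≥1.5 × 10⁹/L, no growth factors | not a listed improvement |
| Marrow | normocellular, no CLL cells or nodules | CLL cells or nodules present, or not done |

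The contrast between CR and PR exists for hemoglobin. For platelets the condition is absent from both columns.

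**Step 2. Does another section close the gap?**

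- The only growth-factor entry on the prohibited list in Section 6.5.1 is "Primary prophylactic G-CSF during the DLT evaluation period". Transfusion and erythropoietin are not on the list.
- Appendix 11 requires hemoglobin to be drawn before a transfusion, but for toxicity grading, and it does not discount the effect of earlier transfusions.
- Sections 6.5 and 8.1.7.2 have medication recorded, with dates and reason, but nothing links those dates to response dates.
- For WM/LPL, by contrast, Section 10.9.3.3 makes a visit not evaluable when every IgM value is confounded by plasmapheresis.

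**Step 3. When does the missing condition decide a PR?** Give each of four Group A parameters three states (normal at baseline, abnormal and improved, abnormal and not improved). Give hemoglobin and platelets four states each (normal, improved unsupported, improved only with support, not improved). Require at least one abnormal Group A parameter. The number of patterns is (3⁴ − 1) × 4² = 80 × 16 = 1,280. These are logical patterns, not probabilities.

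Group A is met in 4 + 6 + 16 + 11 = 37 of the 80 patterns (one, two, three or four parameters abnormal), and every one of them contains a Group A improvement.

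- *Reading A: the marrow line satisfies Group B.* PR as written: 37 × 16 = 592. With a no-support condition on hemoglobin and platelets: still 592. The condition changes nothing, because Group B no longer tests the blood.
- *Reading B: the marrow line is not an improvement.* PR as written: 37 × 13 = 481. With the condition: 37 × 8 = 296. Changed: 37 × 5 = 185.

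The five Group B patterns that change are supported hemoglobin with platelets normal or not improved (2), supported platelets with hemoglobin normal or not improved (2), and both supported (1). A condition on hemoglobin alone would change 37 × 2 = 74 and leave 111 of the 185 as PR through platelets.

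**Step 4. Effect on ORR.** The plan gives no ORR assumption for this study, so there is no figure to reproduce. As a check on the interval method only, the 65 mg CLL/SLL result quoted from BELLWAVE-001 (56.1% of 57, i.e. 32/57) gives 42.4% to 69.3%, as printed.

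One reclassified response moves ORR by 1/n, where n is the number of CLL/SLL participants. Section 1.1 gives about 6 to 12 participants over all histologies and no CLL/SLL count, so n is assumed:

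- n = 3: 1/3 = 33.3 points
- n = 6: 1/6 = 16.7 points. For example, 3/6 = 50.0% (11.8 to 88.2) becomes 2/6 = 33.3% (4.3 to 77.7)
- n = 12: 1/12 = 8.3 points. For example, 6/12 = 50.0% (21.1 to 78.9) becomes 5/12 = 41.7% (15.2 to 72.3)

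If no PR depends on a supported count or on the marrow line, the change is 0.

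**The case against.** The strongest reply is that the protocol applies a published standard as it stands. Section 8.2.1.1 names iwCLL 2018, Section 10.9.1.4 presents its table as a summary of that source, and text and table agree. Tightening PR would then be the reviewer's preference and would make ORR less standard. Part of this stands: the documents cannot show whether the published PR criterion carries the condition, so no departure from iwCLL 2018 is claimed. It does not answer the two internal problems, which are that the protocol rejects supported hemoglobin for CR but is silent for PR, and that a marrow not done is listed as an improvement.

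Four stronger readings are tempting and are not supported:

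- *A supported count alone yields PR.* It does not. Step 3 finds no PR without a Group A improvement.
- *The condition is attached to CR only, for platelets as well.* Platelets have no condition even for CR.
- *Support hides progression and so lengthens DOR and PFS.* A hemoglobin or platelet fall already has to be attributed to CLL before it counts as progression, the nodal, organ, lymphocyte and marrow routes are unaffected, and nothing in the documents sizes an effect.
- *Most anemic entrants are a few units of blood from the threshold.* No baseline distribution is given, and Table 3 waives the floor when marrow involvement is significant.

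It is also fair that recorded medication dates would let growth-factor use be traced at analysis, and that dose decisions rest on DLTs, not on response.

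**Conclusion.** The point holds as a minor ambiguity in a secondary endpoint. As written, Group B can be met by a hemoglobin or platelet value obtained under support, or, on a literal reading of the marrow line, with no blood recovery. The marrow wording is the more consequential of the two, since on that reading the support condition decides nothing.

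ORR can be overstated when Group A is also met. A reader might infer that it is overstated. The documents do not show that, because they give no response data for this study, no transfusion or erythropoietin rate and no CLL/SLL count. The figures of 33.3, 16.7 and 8.3 points are simply 1/n for assumed n of 3, 6 and 12, per reclassified response, and the true effect may be zero. No hypothesis is tested on ORR.

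**What to change.** In Sections 10.9.1.3 and 10.9.1.4:

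1. Attach the condition already used for CR hemoglobin to the PR hemoglobin criterion.
2. State that platelet values obtained under transfusion do not count as Group B improvement for PR.
3. State that the marrow line describes findings compatible with PR and is not itself the improved Group B parameter.
4. Note beside the table that these are clarifications to the cited iwCLL table.

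In the sSAP, define the interval after transfusion or growth factor within which a value is treated as supported, and check recorded transfusion and growth-factor dates against response dates. Confirm that transfusions are captured with dates, since Section 6.5 speaks of medications and vaccines. Say also how a visit with only supported values is scored. Scoring it as assessed but not improved keeps it from becoming not evaluable and then, under the missing-data rule of Section 9.6.2, a non-response by default.

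These changes concern how response is scored and do not alter supportive care. The cost is a few lines of appendix text and one data check. ORR may be slightly lower, and slightly less comparable with studies that use the unmodified table.
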